### 5.1. *Scale and Duration*

A total of 415 subjects will be included in the study to ensure a minimum of 329 TREATMENT subjects.

The study is global and will include 25-50 sites in the United States, Europe and Asia-Pacific. A minimum of 50% of the sites will be selected from the United States.

To reduce the impact of individual center bias, no study site will be allowed to contribute more than 41 subjects (10% of the 415 enrollments requirement).

Each subject will be followed at specified time points after the ablation procedure (index procedure) with a follow-up duration of three years. A study subject's participation will be considered complete when all protocol required visits have been completed as indicated in Figure 5.2-1.

Accordingly, the study is expected to be completed in approximately five years (two-year enrollment period with three-year follow-up).

[figure not shown]

Figure 5.1-1: INTERRUPT AF Study Design

Table 2: INTERRUPT AF Study Timeline

Milestone	Forecast Date
Start	Upon FDA approval of PAS Protocol
First Enrollment	Approximately 120 days after FDA approval of the protocol
Enrollment Plan	Given the global prevalence of Paroxysmal Atrial Fibrillation, it is estimated that each activated site can each enroll 1 subject per month. It is anticipated that it will take 12-24 months to enroll the 415 subjects.
Progress Updates	Progress reports will be provided every six months for the first two years from the date of FDA Approval of PAS Protocol , then annually thereafter. Section 9.3.1 contains details of the progress report content.
Primary Objective Analysis	Within 3 months of 12-Month Visit Completion for all subjects.
Final Post Approval Study Report	Within 3 months of 36-Month Visit Completion for all subjects.

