### ***7.2. Withdrawal***

All subjects enrolled in the clinical study (including those withdrawn from the clinical study) shall be accounted for and documented. If a subject withdraws from the INTERRUPT AF study, the reason(s) shall be reported.

Reasons for withdrawal may include physician discretion, change in inclusion/exclusion status, subject choice to withdraw consent, lost to follow-up, or death. While study withdrawal is discouraged, subjects may withdraw from the study at any time, with or without reason, and without prejudice to further treatment. All applicable electronic case report forms (eCRFs) up to the point of subject withdrawal and an “End of Study” eCRF must be completed. For subjects who are “lost to follow-up” the investigator/center should have at least three documented attempts to contact the subject prior to completion of the “End of Study” eCRF. No additional data may be collected after a subject has been withdrawn from the study or withdraws his/her consent, for whatever reason. All open adverse events should be closed or documented as chronic. Data collected up to the point of subject withdrawal may be used. If such withdrawal is due to problems related to device safety or performance, the investigator shall ask for the subject’s permission to follow his/her status/condition.

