### ***7.3. Subject Status and Classification***

All enrolled subjects will be classified into one of three categories based on their progress and completion of key events. Classification will determine how data gathered from them will be stored and evaluated.

- **INTENT**: Any subject that signs the consent form but does not have any study devices inserted into the body. Subjects who are enrolled in the study but do not undergo ablation procedure within 60 days from consent signature date may not be reconsented and will be withdrawn from the study and classified as “INTENT”. INTENT subjects will count towards the enrollment ceiling and will not be used for analysis of the endpoints. INTENT subjects will not be followed for any additional visits after withdrawal. For these subjects an “End of Study” form must be completed. The original signed Informed Consent must be maintained in the center’s subject file.
- **ATTEMPT**: Any subject that signs the consent form, meets eligibility criteria and has any protocol defined study device inserted into the body but does not receive RF ablation per protocol. Additionally, any subject not treated with a BSC OI Catheter **and** the Rhythmia System will be considered an ATTEMPT. Use of the IntellaMap Orion Catheter is required but will not affect subject classification. Procedures that do not utilize the IntellaMap Orion Catheter will have a protocol deviation entered. Subjects will be followed for one month for safety reporting only. Therefore, ATTEMPT subjects will not be assigned an event monitor for study purposes. All applicable case report forms must be completed, including Baseline, data pertaining to the Index

procedure, Adverse Event reporting and one-month follow-up. ATTEMPT subjects will count towards the enrollment ceiling and will not be used for analyses of the primary endpoint. The original signed Informed Consent must be maintained in the center's study file.

- **TREATMENT:** Any subject that signs the consent form, meets eligibility criteria and has the specified study devices inserted into the body and undergoes protocol specific treatment for the intended disease.

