3.4 Tertiary endpoint

Chronic Effectiveness: Evaluation of chronic recurrence at 24 months and 36 months

- Recurrence is defined as intervention for atrial fibrillation, or new onset of atrial flutter or atrial tachycardia (repeat procedures, use of AADs, cardioversion), excluding repeat procedures during the 90-day blanking period.
- Data collection to include the diagnostic modality used to identify recurrence and the therapeutic intervention
- Chronic effectiveness will be evaluated using Kaplan-Meier methodology. The Kaplan-Meier 24 month and 36 month chronic recurrence-free rate will be calculated and presented along with the 95% confidence interval, calculated as the pointwise confidence limit using the log-log methodology. Subjects who die or withdraw from the study prior to the specified time point without experiencing an event will be censored on the date of death or on the date of withdrawal.

Center Experience: Primary safety and Primary effectiveness outcomes by center experience

- In order to evaluate training effectiveness for investigators outside of the ZERO AF IDE study, outcomes in centers performing five or more procedures using the Blazer OI catheter during the ZERO AF IDE study will be compared to all other. Kaplan-Meier rates and 95% confidence intervals for the Primary Safety and Effectiveness endpoints for both groups will be presented with no statistical comparison.

Safety: Reportable Adverse Events rates at 12, 24 and 36 months

Adverse events will be collected at all subject follow-up visits. Reportable events include:

- All Serious Adverse Events
- All Study Procedure-Related Adverse Events
- All Study Device-Related Adverse Events
- All Study Device Deficiencies
- Unanticipated Adverse Device Effects/Unanticipated Serious Adverse Device Effects previously not defined in the Directions For Use.

Adverse event rates will be calculated using binomial methodology. The cumulative number of events and event rate will be included in all study reports. Subjects at risk for an adverse event will be determined by the subject treatment status; all treatment and attempt subjects will be considered at risk for study related adverse events

Effectiveness: Acute Procedural Success Rate

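### Binomial adverse event rates at 12, 24 and 36 months take no account of follow-up time, so rates of late events, mainly all-cause SAEs at 24 and 36 months, are understated

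*SAP*

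**What the plan says.** The tertiary safety item in SAP 3.4 is headed "Safety: Reportable Adverse Events rates at 12, 24 and 36 months"; Protocol 4.4 and 9.1.4 match it. The estimator is given in one sentence: "Adverse event rates will be calculated using binomial methodology". The denominator is given in the next lines: "Subjects at risk for an adverse event will be determined by the subject treatment status", and then "all treatment and attempt subjects will be considered at risk for study related adverse events". The events covered go beyond related ones, since the list opens with "All Serious Adverse Events".

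Follow-up differs by class. Protocol 5.1 plans follow-up of each subject "with a follow-up duration of three years", but for ATTEMPT subjects Protocol 7.3 says "Subjects will be followed for one month for safety reporting only". Protocol 7.2 adds: "No additional data may be collected after a subject has been withdrawn from the study or withdraws his/her consent, for whatever reason".

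Neither document gives these rates a censoring rule, a denominator restricted to subjects still followed, person-time, or a time-to-event estimate. In the same SAP section, 24- and 36-month recurrence is estimated by Kaplan-Meier, with censoring at death or withdrawal. SAP 3.1.3 uses Kaplan-Meier for primary safety.

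**The concern.** A binomial proportion at 36 months estimates 36-month incidence only if everyone in the denominator was observed for 36 months or had the event first. Here an ATTEMPT subject can contribute an event in month 1 and none later. A TREATMENT subject who withdraws can contribute none afterwards. Those who leave without an event stay in the denominator as non-events. If leaving is unrelated to risk, the error runs one way, towards lower rates, and grows with the time horizon.

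Protocol 2.2 gives safety through three years as a purpose of this post-approval study. These rates are the planned summary of adverse events beyond 12 months, because the primary safety analysis stops there.

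**Working it through.** **Inputs from the documents.** Attrition is 7.5% per year (SAP 3.1.2, a planning value for a 12-month endpoint). ATTEMPT follow-up is one month (Protocol 7.3). Enrolment is 415, with at least 329 TREATMENT (Protocol 9.1.5).

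**The plan's own figure.** No figure is stated for the adverse event rates. The 7.5% does enter the primary safety sample size. An exact binomial test of 90% against 85% (one-sided 5%) needs 304 subjects for power to stay at or above 80%, and 304/0.925 = 328.6, which rounds up to the stated 329. So 7.5% means that 92.5% remain after one year.

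**Retention if that rate continues.** 0.925, 0.925² = 0.856 and 0.925³ = 0.791 at 12, 24 and 36 months, so about 21% are lost by 36 months.

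**Assumptions.** None of these is in the documents:
- Incidence in month 1 is p = 8%, with a constant event hazard h afterwards.
- Loss is exponential at rate c = -ln(0.925) = 0.0780 per year and unrelated to risk.
- The ATTEMPT share s is 0 to 10%. The documents only bound INTENT and ATTEMPT together, at 415 - 329 = 86, or 20.7% of enrolment.

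**Formulas.** With F the true 36-month incidence and T in years:
- h = ln[(1 - p)/(1 - F)] / (35/12)
- True incidence at T = 1 - (1 - p)·exp[-h(T - 1/12)]
- Crude TREATMENT proportion = p + (1 - p)·exp(-c/12)·[h/(h + c)]·{1 - exp[-(h + c)(T - 1/12)]}
- Crude ATTEMPT proportion = p
- Reported rate = (1 - s)·TREATMENT + s·ATTEMPT

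**Worked case, F = 30%, T = 3.** h = ln(0.92/0.70)/2.917 = 0.0937. Crude TREATMENT = 0.08 + 0.92 × 0.9935 × 0.5458 × 0.3939 = 27.7%. With s = 10%: 0.9 × 27.65% + 0.1 × 8% = 25.7%.

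| True 36-month rate | Time (months) | True | Crude, s = 0 | Crude, s = 10% | Relative understatement |
|---|---|---|---|---|---|
| 10% | 12 | 8.6% | 8.6% | 8.6% | 0.3-1.0% |
| 10% | 24 | 9.3% | 9.2% | 9.1% | 1.1-2.4% |
| 10% | 36 | 10.0% | 9.8% | 9.6% | 2.2-4.0% |
| 30% | 12 | 15.6% | 15.3% | 14.5% | 2.0-6.6% |
| 30% | 24 | 23.1% | 22.0% | 20.6% | 4.9-11.0% |
| 30% | 36 | 30.0% | 27.7% | 25.7% | 7.8-14.4% |
| 40% | 36 | 40.0% | 36.7% | 33.8% | 8.3-15.5% |

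**Sensitivity to event timing.** Take a true 36-month rate of 20% and s from 0 to 10%. With a constant hazard from day 0 and no early peak, the crude 36-month rate is 17.9% to 16.2%, an understatement of about 10-19%. If 80% of the events fall within 7 days of the procedure, it is about 2-4%. If 95% do, it is 1% or less.

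**The case against.** The strongest objection is about scope. The explicit TREATMENT plus ATTEMPT denominator is worded for study-related events only. Those are probably mostly peri-procedural (the primary safety composite is mainly a 7-day list), and for them the bias is a few per cent at most. A 36-month incidence of 30-40% is plausible only for all-cause SAEs, whose denominator is set by treatment status without saying which classes count. This stands. A reader might infer that every reportable rate is divided by all TREATMENT and ATTEMPT subjects and is 8-16% too low; the documents support neither. If ATTEMPT subjects are left out of the all-cause denominator, the s = 0 column applies, and withdrawals alone still give about 8% at 36 months in the 30% and 40% cases.

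A second objection is that primary safety is already protected by Kaplan-Meier with censoring, a tipping-point analysis (SAP 5.6.1) and Kaplan-Meier in the interim reports (SAP 5.1). That is correct, so a reader should not infer that the primary safety conclusion is biased by this choice. But those analyses cover the primary safety events, which run to 12 months at most, and do nothing for the 24- and 36-month adverse event rates.

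A third is that the size rests on assumed inputs. This also stands: the direction is secure if loss is unrelated to risk, but the size is not.

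**Conclusion.** The point holds for late events, mainly all-cause SAEs at 24 and 36 months. As written, the method counts subjects who leave without an event as event-free for unobserved time. Subjects with an event before leaving are counted correctly.

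Given 8% incidence in month 1, 7.5% annual loss carried to 36 months and 0-10% ATTEMPT subjects, the relative understatement at 36 months is about 2-4% when most events are early (true rate 10%) and about 8-16% when many are late (true rate 30-40%). At 12 months it is about 2-7% in the 30% case. It would be larger with a higher ATTEMPT share and smaller with better retention.

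The endpoint is descriptive, with no hypothesis or performance goal. The primary safety test, its sample size and study success do not change.

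**What to change.** In SAP 3.4 and Protocol 4.4 and 9.1.4:
- Report the 12-, 24- and 36-month incidence of SAEs, and separately of procedure- or device-related AEs, as 1 minus Kaplan-Meier or as cumulative incidence with death as a competing event. Give log-log confidence limits and numbers at risk. Protocol 15.1 records a death as the outcome of an SAE, so the competing-event choice matters mainly for related AEs.
- Keep ATTEMPT subjects in, censored at their one-month exit. Censor withdrawals at the date of withdrawal. ATTEMPT subjects need not be removed, and the plan's inclusion of everyone exposed to a study device is kept.
- State which subject classes are at risk for events that are not study-related.
- Keep crude counts and binomial proportions for the peri-procedural window and for device deficiencies, which Protocol 15.5 does not class as adverse events.

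The cost is revised wording, one extra table and slightly less favourable long-term rates. No new data, visits or subjects are needed.

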4 GENERAL STATISTICAL METHOD

4.1 Analysis Sets

While each endpoint was individually powered, each endpoint analysis will use all available data from all eligible subjects, regardless of original calculated sample size.

4.2 Control of Systematic Error/Bias

Selection of patients will be made from the Investigator's usual patient load. All patients meeting the eligibility criteria and having signed the ICF will be eligible for enrollment in the study.

4.3 Study Success and Control of Type I Error

Each primary endpoint can be tested at the significance level of 5% while still maintaining the overall type I error level at no greater than 5%. This follows the methodology of the Intersection-Union Test (IUT). If both primary endpoints are passed then a gating approach will be employed to test the secondary effectiveness endpoint at a significance level of 5%.

4.4 Number of Subjects per Investigative Site

To avoid any center effect and bias, one center will not be authorized to enroll more than 41 subjects (10% of the 415 enrollment total).

5 ADDITIONAL DATA ANALYSES

5.1 Interim Analyses and Progress Report Content

No formal interim analyses are planned for the purpose of stopping the study early for declaring effectiveness or for futility. Analysis of each endpoint will be performed when all applicable data for that endpoint has been collected. Analysis of the 12-month endpoints (Primary Safety, Primary Effectiveness, Secondary Effectiveness and all additional analyses pertaining to these endpoints) will be included in a Primary Endpoint Report. Additionally, Kaplan-Meier analyses for the Primary Safety Endpoint events using all available data at the time of the report will be included in interim progress reports to the FDA. These analyses will use the same definition of safety events used in the Primary Safety Endpoint but will censor active subjects who have not experienced an endpoint event and have not completed their 12-month follow-up on the day of the data snapshot.

Progress reports will be provided to the FDA every 6 months for the first two years and annually thereafter. Reports will include sections outlined in the relevant FDA guidance pertaining to Post Approval Studies. At minimum, the progress reports will contain the following:

- Number of study sites with enrolled subjects
- Summary of subject enrollment, subject status, and demographics
- Analysis of Primary Safety Endpoint events
- Summary of adverse events, deaths, deviations, and device deficiencies

Results from the progress reports will be posted on the FDA PAS website (https://www.accessdata.fda.gov/scripts/cdrh/cfdocs/cfPMA/pma_pas.cfm).

Field Code Changed

5.2 Subgroup Analyses

An analysis will be performed for the primary endpoints to determine whether significant differences exist in endpoint results between subgroups. The list of covariates (with applicable subgroups in parentheses) includes the following:

- Sex (Female vs. Male)
- Age at time of consent (subjects > 60 years vs subjects \leq 60 years and subjects > 70 years vs subjects \leq 70)
- Repeat procedures in the blanking period (Repeat procedure within 90 days of index procedure vs. no repeat procedure within 90 days of index procedure)
- Ablation technique (PVI only vs. PVI + additional ablations)
- Use of device features (DirectSense used in the index procedure vs DirectSense not used in the index procedure).

Each subgroup covariate will be included as a single independent variable in a logistic regression model with the primary endpoint outcome as the dependent variable and a test for significance at the 15% level will be performed.

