### ***8.14. Repeat Ablation Procedure***

It is known that a repeat ablation procedure may be necessary in certain subjects after the index ablation procedure due to recurrences of PAF or other tachyarrhythmias requiring treatment. One repeat procedure is allowed within the blanking period if considered medically necessary due to subject's intolerance of the arrhythmia. Data collection requirements for the repeat procedure are the same as those for the index procedure.

If an investigator believes it is in the subject's best interest to perform the ablation with a non-study catheter, the investigator may choose to withdraw the subject from the study prior to performing the procedure. Prior to study withdrawal and undergoing the repeat procedure with a different (non-study) catheter, imaging of the PVs is required. The appropriate type of imaging performed may be determined by the investigator. As available, the PV images must be reviewed against the pre-ablation imaging from the index procedure to rule out PV stenosis from the index ablation procedure. In addition, repeat ablation with a non-study catheter must occur  $\geq 30$  days after the previous ablation procedure.

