3.1 Primary Safety Endpoint

Safety will be evaluated by the primary safety event free rate at 12 months post procedure. Primary safety events will consist of a composite of acute primary safety events (events occurring within seven days post-procedure or hospital discharge, whichever is later), and chronic primary safety events (events occurring through 3 or 12 months post-procedure).

Acute primary safety events will be defined as the following:

- Death
- Myocardial infarction (MI)
- Vagal Nerve Injury/Gastroparesis
- Transient ischemic attack (TIA)
- Stroke/Cerebrovascular accident (CVA)
- Thromboembolism
- Pericarditis
- Cardiac tamponade/perforation
- Pneumothorax
- Vascular access complications
- Pulmonary edema/heart failure
- AV block

Chronic primary safety events will be defined as the following:

- Occurring through 3 Months post-procedure
 - Atrial esophageal fistula

- Pericardial effusion
- Occurring through 12 Months post-procedure
- Pulmonary vein stenosis (symptomatic and requiring intervention)

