3.2 Primary Effectiveness Endpoint

The primary effectiveness endpoint will be evaluated by the primary effectiveness event-free rate at 12 months post-procedure.

Primary effectiveness events will be defined as the following:

- Acute procedural failure
- More than one repeat procedure during the blanking period (90 days post index procedure)
- Documented atrial fibrillation, or new onset of atrial flutter or atrial tachycardia event (≥ 30 seconds in duration from an event monitor or Holter Monitor, or from a 10 second 12-lead EKG) between 91 days and 365 days post index procedure
- Any of the following interventions for atrial fibrillation, or new onset of atrial flutter or atrial tachycardia between 91 days and 365 days post index procedure:
 - Repeat procedure
 - Cardioversion
 - Prescribed any AAD*

*AADs for endpoint will consist of all Class I/III and any Class II/IV medications taken for control of AF/AT/AFL recurrence

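### For primary effectiveness, the blanking-period repeat subgroup partly overlaps with the endpoint, which biases the comparison toward more failures among repeaters; a day-91 landmark removes this

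*SAP*

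**What the plan says.** SAP 5.2 sets the aim: "An analysis will be performed for the primary endpoints to determine whether significant differences exist in endpoint results between subgroups". One of the five covariates is "Repeat procedure within 90 days of index procedure vs. no repeat procedure within 90 days of index procedure". On the method: "Each subgroup covariate will be included as a single independent variable in a logistic regression model". What is modelled is each subject's result on the primary endpoint, and the test level is 15%. Protocol 9.3.2 has the same text.

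The primary effectiveness endpoint (SAP 3.2) has two kinds of event that are settled before day 91: "Acute procedural failure" and "More than one repeat procedure during the blanking period (90 days post index procedure". Its other events, documented arrhythmia and interventions, count "between 91 days and 365 days post index procedure".

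A single early repeat is not an event. Protocol 8.14 states: "One repeat procedure is allowed within the blanking period if considered medically necessary". The blanking-period definition in Protocol Table 11 agrees.

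The primary safety composite (SAP 3.1) has no repeat-procedure component. Its acute components cover "events occurring within seven days post-procedure or hospital discharge, whichever is later". Effusion and atrio-esophageal fistula count through 3 months, and pulmonary vein stenosis through 12 months.

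Neither document sets a landmark, excludes subjects who have failed by day 90, or warns that this grouping is fixed after the index procedure.

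**The concern.** The other four covariates (sex, age, ablation technique, DirectSense use) are known by the end of the index procedure. This one takes up to 90 more days to settle, while the outcome is counted from day 0.

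For effectiveness the two overlap. Every subject with a second blanking-period repeat is both a repeater and a failure, and none can be in the comparison group. Acute procedural failure adds a less direct route: it is a failure at day 0, and such a subject may be more likely to be brought back early.

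Both routes push the repeat group's failure rate up for reasons unrelated to what happens after blanking. At stake is the reading of one subgroup result in the Primary Endpoint Report. A reader would naturally take a significant result to mean that patients who needed an early repeat do worse afterwards, and the planned test cannot separate that from the overlap.

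**Working it through.** **The plan's own figure.** The documents give no figure for this subgroup test. The one they supply for it is the 329 TREATMENT subjects in SAP 3.1.2 (90% expected against 85%, one-sided 5%, 80% power, 7.5% attrition). The exact binomial calculation needs 304 subjects (the smallest n from which power stays at or above 80%), and 304/0.925 = 328.6, so 329. The plain normal approximation gives 283, and 283/0.925 = 306. The 329 therefore reproduces by the exact method, and the choice of method does not bear on this point.

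**Inputs from the documents.** N = 329; test level 15%, taken as two-sided; expected effectiveness event-free rate 60% (SAP 3.2.2), so about 40% failure.

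**Assumptions, because the documents are silent.** The repeated share r is 5–15% (16, 33 or 49 of 329). The share s of repeaters with a second blanking-period repeat is 0–20%. The test is the likelihood-ratio test, since the SAP does not say Wald or likelihood ratio. Every subject has a complete binary outcome.

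**Direct overlap.** Let the day 91–365 failure risk be f = 0.40 in both groups. Then:

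- P(fail | no repeat) = f = 40%
- P(fail | repeat) = s + (1 − s)f

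At s = 10% this is 0.10 + 0.90 × 0.40 = 46%, an odds ratio of (0.46/0.54)/(0.40/0.60) = 1.28. At s = 20% it is 0.20 + 0.80 × 0.40 = 52%, an odds ratio of 1.62. The rejection probability is summed exactly over the two binomial distributions.

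| Share repeated twice, s | Failure, repeat vs none | Rejects, r = 5% | r = 10% | r = 15% |
|---|---|---|---|---|
| 0 | 40% vs 40% | 15% | 15% | 15% |
| 5% | 43% vs 40% | 17% | 18% | 18% |
| 10% | 46% vs 40% | 20% | 24% | 27% |
| 20% | 52% vs 40% | 32% | 46% | 55% |

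With 33 repeaters, s = 10% is about 3 subjects and s = 20% about 7.

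**Indirect route through acute failure, with no second repeats.** Let a be the acute failure rate and k the ratio of repeat probability in acute failures to that in other subjects. Then:

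- acute failures among repeaters: a₁ = ak/(ak + 1 − a)
- acute failures among non-repeaters: a₀ = (a − r·a₁)/(1 − r)

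Take a later risk of 37% in both groups, so that overall failure stays near 40% (0.05 + 0.95 × 0.37 = 40.2%). For a = 5%, k = 3 and r = 10%:

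- a₁ = 0.15/1.10 = 13.6% and a₀ = (0.05 − 0.0136)/0.90 = 4.0%
- failure is 0.136 + 0.864 × 0.37 = 45.6% against 0.040 + 0.960 × 0.37 = 39.5%
- the test rejects 24% of the time

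Over a = 2–5%, k = 3–5 and r = 5–10%, rejection runs from 16% to 42%. All of these inputs are assumed.

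**Safety.** There is no overlap term, so both groups carry the same 10% risk. The likelihood-ratio test rejects 25%, 17% and 16% of the time at r = 5%, 10% and 15%. The excess over 15% comes from sparse counts: with 16 repeaters, the chance of no events is 0.9¹⁶ = 18.5%, and zero events already gives a significant statistic.

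**After the fix.** Drop everyone who has failed by day 90, then compare one repeat with none. With 40% later risk in both groups, the test rejects 15–16% of the time for r = 5–15%, including when 10–20% of the repeat group has been removed. That is essentially its nominal level.

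**The case against.** The strongest reply is that SAP 5.2 asks only whether endpoint results differ between subgroups. If repeaters have more endpoint failures as the endpoint is defined, that is a real difference in the composite, and rejecting is correct. This stands as a reading of the text: the rejection rates above are false positives only for the question whether later risk differs. But a difference produced by counting second repeats as failures tells the reader nothing beyond the definition, and the SAP does not say that the result should be read so narrowly.

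Second, the direct overlap needs a procedure beyond the one repeat that the protocol allows. With no second repeats, and acute failure unrelated to repeating, the test keeps its level. This also stands. Nothing in the documents supports a second-repeat share of 10–20%.

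Third, a reader might infer that the planned test will show a significant difference. The figures do not support that: at s = 10% it shows none about three times in four, and at s = 20% it rejects more than half the time only toward the upper end of the assumed repeat rates.

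Fourth, a reader might extend the criticism to safety, arguing that nearly all safety events fall in the first week, before any repeat, and that the covariate should be dropped there. Neither document says how events are spread over time. Three components run to 3 or 12 months and can follow a repeat. Dropping the covariate would also remove a planned look at safety events in subjects ablated twice. What remains for safety is a timing caution.

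Early loss to follow-up, which keeps a subject out of the repeat group, is small: at 7.5% per year, 1 − 0.925^(90/365) = 1.9% by day 90.

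**Conclusion.** The point holds for primary effectiveness. The subgroup is defined after the index procedure and shares subjects with the endpoint by construction, so the comparison leans toward more failures in the repeat group even when day 91–365 risk is equal. The direction is certain as soon as anyone has a second blanking-period repeat. The size is not known: it rests on assumed repeat and second-repeat shares, and it ranges from no effect, through a few points of excess rejection, to a test that rejects about half the time at the far end.

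For primary safety there is no definitional overlap, only a grouping that some events may precede.

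This is a minor point. Success requires only the two primary tests, with the secondary endpoint gated behind them (SAP 3 and 4.3), and no decision rule is attached to the subgroup result. A reader should not infer any effect on the study's conclusions.

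**What to change.** For primary effectiveness, define this one subgroup analysis from a day-91 landmark in SAP 5.2. Include TREATMENT subjects who are event-free and in follow-up at day 91, group them by one blanking-period repeat versus none, and compare primary effectiveness events from day 91 to day 365. Requiring follow-up at day 91 also deals with subjects withdrawn before a non-study-catheter repeat (Protocol 8.14), whose repeat may go unrecorded because data collection stops at withdrawal (Protocol 7.2).

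For primary safety, keep the comparison but label it descriptive, with a note that the grouping is post-index and that some events may precede the repeat.

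The cost is SAP wording, which SAP 6 allows by amendment before the analysis is run, and slightly fewer subjects. If attrition by day 90 is 1.9%, acute failure 2–5% and second repeats 1% (10% of 10%), the loss is about 5–8% of 329, or 16–26 subjects.

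The landmark result describes post-blanking risk only. It still cannot be read as the effect of a repeat, because repeats are done for early recurrence.
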